6.1. Schema

Patients scheduled to undergo percutaneous cardiac intervention procedures in which VeriSight will be used for imaging and are willing to participate in the registry may be enrolled. Subjects will be enrolled at up to 10 clinical sites in the United States. Patients who are indicated for the use of VeriSight per the commercial IFU will be screened for registry participation at the screening/baseline visit, and enrolled subjects will be evaluated on the day of the procedure and again within discharge or ≤48 hours post-procedure (whichever is first), as per site's standard of care. Figure 1 provides an overview of the registry procedures at each visit.

[figure not shown]

Figure 1. Study flow diagram

6.2. Schedule of Activities (SOA)

Table 1 provides an overview of registry procedures per visit.

Document ID:	IGT_IGD_ICE Registry Study_2019_10745	Document title:		Classification:	Confidential
Modified:	24 APR 2021	Philips ICE Registry			
Version:	2.0	User Tool ID:	16.2.6UserTool0004	Page:	19
Status:	Final	User Tool Version Date	30May2019		

Clinical Registry Protocol
IGT_IGD_ICE Registry Study_2019_10745

Table 1. Overview of registry procedure			
Procedures	Screening*	Index procedure	Post-Procedure (at discharge or 48hrs)
Assessment of eligibility	X		
Informed consent	X		
Record demographics	X		
Medical History and Physical (H&P)	X		
Record any baseline diagnostic imaging		X	
ICE imaging with VeriSight		X	
Image grading		X	
Procedural workflow and details		X	
Adverse device effects related to VeriSight		X	X
Registry exit			X
Usability assessment	Aggregate input		
Physical attributes of catheter	After 1 st patient enrolled	After 10 th patient enrolled	After last patient enrolled
Physician and staff survey	After 1 st patient enrolled	After 10 th patient enrolled	After last patient enrolled

*up to 30 days prior to index

Below are the brief study procedure steps.

- Subjects are evaluated for eligibility based on the inclusion and exclusion criteria
- Record demographics of subjects: age, gender, height, weight, ethnicity/race (if applicable)
- Record relevant medical and surgical histories
- The subjects will be imaged using the VeriSight device according to the routine workflows
- Relevant imaging for each procedural steps will be recorded.
- The Investigator will grade the imaging recorded
- The corresponding clinical information and information about the use of device and system, including device deficiencies and safety-related adverse device effects related to VeriSight, will be recorded by the Investigator in the CRF
- The registry examinations including all collected de-identified images will be transferred to Philips

Document ID:	IGT_IGD_ICE Registry Study_2019_10745	Document title:		Classification:	Confidential
Modified:	24 APR 2021	Philips ICE Registry			
Version:	2.0	User Tool ID:	16.2.6UserTool0004	Page:	20
Status:	Final	User Tool Version Date	30May2019		

Clinical Registry Protocol
IGT_IGD_ICE Registry Study_2019_10745

- After the completion of the procedure, subject are dismissed from the registry after monitoring for post-procedure adverse device effects either at discharge or ≤48 hrs post-procedure, whichever is sooner.

6.3. Screening (up to 30 days prior to index procedure)

This visit consists of screening and enrollment activities and may also include any pre-procedural planning in accordance with standard practice and local institution protocol. Subjects will be recruited from a pool of regular patient population that are eligible for percutaneous cardiac intervention procedure. This visit will consist of the following procedures.

Assessment of Eligibility

The Investigator will assess the subject's eligibility for this study per the inclusion and exclusion criteria listed in **Section 4.0** and will document the outcome of the eligibility assessment. If the subject qualifies, he or she will then undergo the registry-related imaging examinations described below. The investigator shall screen the patient and deem them suitable for conducting the procedure under conscious sedation.

Informed Consent

Study participation is voluntary. The potential subject if deemed eligible for the study based on the known information in the medical records, will be informed about the study and asked to participate. He/she will be given the most current IRB-approved Informed Consent Form (ICF) to read. Ample time will be provided for review and an opportunity to ask questions about the study. If the subject agrees to participate, they will sign the ICF and be given a copy of the signed document for their records. All components of the consent process will be documented in source documents. A detailed description of the consent process is provided in **Section 9.2**.

Medical History and Demographics

Standard subject demographics (e.g. age, gender, race, ethnicity, height, weight), relevant medical and surgical histories will be recorded. The assessments will be performed following the institutions' standard protocols and the results recorded on the appropriate subject case report forms. Any pertinent diagnostic imaging as it relates to the index procedure (e.g. CT, MRI, TTE) if performed per standard institutional protocol will be documented.

New information about the study

As the subject will exit registry at discharge, or ≤48 hrs post-procedure, whichever is earlier, it is unlikely that any new information will influence a subject's decision to participate. However, as ultrasound technology is constantly evolving it may be necessary from time to time to update the ICF so the subject may be informed of any new information. This will be done in conjunction with IRB approval, as appropriate.

Document ID:	IGT_IGD_ICE Registry Study_2019_10745	Document title:		Classification:	Confidential
Modified:	24 APR 2021	Philips ICE Registry			
Version:	2.0	User Tool ID:	16.2.6UserTool0004	Page:	21
Status:	Final	User Tool Version Date	30May2019		

6.4. Index Procedure

Subjects enrolled in the registry will undergo imaging using the VeriSight catheter at the time of the index procedure. This visit will consist of the following procedures.

The indication for ICE imaging and the types of procedures that utilized VeriSight will be documented. Patient management and treatment decisions are at the discretion of the care team per routine standard clinical practice. The model of VeriSight and the venous access approach are to be per the investigator's discretion. Confirmation of the delivery of the VeriSight catheter to reach the target intracardiac anatomical position including the number of attempts depending on the procedure type will be recorded. The sustained operation of the catheter will be monitored throughout the case and recorded as part of the device technical complications including device malfunction/ deficiency and any additional procedural delays/ disruption when using VeriSight for various procedures.

Clinical data on the imaging views obtained during the procedure will be obtained. The angle of the views (0, 45, 90, 135 sweep) including axis, and the use of xPlane, iRotate, 2D or 3D, TrueVue, MultiVue modalities are left to the investigator's discretion. The anatomical landmarks for image quality assessment depend on the procedure type. Image acquisitions of cardiac structures with VeriSight shall be recorded depending on the procedure type.

The sequence of imaging for each procedure type are according to physician workflow preference. The method and access to the left atrium including transseptal puncture depending on the procedure type are to be per the investigator's discretion. For each procedure labeled screenshots and respective measurements will be documented for key procedural steps. The number of great vessels and chambers imaged will be documented. Sizing relevant anatomy for intervention or device placement and visualization, guidance and verification for delivery and/or placement of interventional device will also be noted in the case report form. Imaging with VeriSight for visualization and evaluation of intra-procedural complications and hemodynamic monitoring will be captured. Images obtained from different procedure types will be reviewed by the participating investigators at regular intervals as part of ongoing development of standard of care workflow with VeriSight ICE imaging.

6.5. Post-procedure

Patients will be followed up until discharge or until ≤48 hours post procedure whichever is earlier. Adverse device effects related with the use of the VeriSight device will be captured in the case report form during this visit as defined in **Section 7.0**.

6.6. Usability Assessments during Index Procedure

Physical attributes of Catheter evaluation method

The evaluation of the physical attributes of the catheter such as catheter handling characteristics, EPIQ system navigation, and imaging modality will be assessed at specific enrollment stages at each participating site: after first patient enrolled, 10th patient enrolled, and last patient enrolled. Evaluation of response will be captured via a scoring scale (poor, average, good, excellent) based on experience acquired with VeriSight in this registry.

The participating investigator will evaluate the same physical characteristics of the catheter, ultrasound system navigation, and imaging modality based on their own clinical experiences of imaging that would have been generally used during the procedure. This rating score is defined as inferior, better, superior and will be gathered at first enrollment, 10th enrollment, and last enrollment at each participating site.

Document ID:	IGT_IGD_ICE Registry Study 2019 10745	Document title:		Classification:	Confidential
Modified:	24 APR 2021	Philips ICE Registry			
Version:	2.0	User Tool ID:	16.2.6UserTool0004	Page:	23
Status:	Final	User Tool Version Date	30May2019		

Physician and staff survey

Physician and staff evaluations regarding Philips ICE will be collected at first enrollment, 10th enrollment, and last enrollment at each participating site. The survey will consist of a series of claim statements ("stimuli"), each of which will be presented alongside a five-point ordinal Likert-type rating scale that will be evaluated by the participating investigator using the knowledge and experience acquired during the registry, and additionally individual clinical experience working with other ICE products or imaging modalities (e.g., TEE).

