Planned Enrollment	Up to 200 patients scheduled to undergo cardiac interventional percutaneous procedures for which ICE is indicated. Interim analysis is planned after the 100 th patient before further continuity of enrollment in the registry.
Registry Sites	Up to 10 sites in the United States with a maximum enrollment of no more than 30% patients at each participating site
Registry Exit	Either at discharge or ≤48 hours post-procedure, whichever is earlier
Registry Duration	Duration of the registry is estimated to be approximately 24 – 36 months.
Statistical Methodology	No hypothesis testing is planned. All subjects enrolled in the study will be accounted for in the study report. Descriptive statistics and 95% confidence intervals will be calculated for variables.

Document ID:	IGT_IGD_ICE Registry Study_2019_10745	Document title:	Classification:	Confidential	
Modified:	24 APR 2021	Philips ICE Registry			
Version:	2.0	User Tool ID:	16.2.6UserTool0004	Page:	9
Status:	Final	User Tool Version Date	30May2019		

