3. REGISTRY DESIGN

3.1. General Description

This is a prospective, multi-center, observational, single-arm registry intended to gather real-world data to report VeriSight ICE catheter performance and safety. It will be conducted in the United States under the approval of one or more recognized institutional review boards and in compliance with GCP guidelines defined in ISO:14155:2011, the Declaration of Helsinki, and all applicable federal and local laws and regulations. Only on label uses of the VeriSight ICE catheter will be allowed. No specific claims are being validated during this registry, though data analyzed from this protocol are intended to inform of future claims regarding the performance and safety of the VeriSight catheter.

Document ID:	IGT_IGD_ICE Registry Study 2019 10745	Document title:		Classification:	Confidential
Modified:	24 APR 2021	Philips ICE Registry			
Version:	2.0	User Tool ID:	16.2.6UserTool0004		
Status:	Final	User Tool Version Date	30May2019	Page:	14

Clinical Registry Protocol
IGT_IGD_ICE Registry Study_2019_10745

Enrolled patients will be imaged with VeriSight for various types of percutaneous cardiac interventional procedures. Enrolled subjects will be followed until discharge or ≤48 hrs post-procedure. The registry has a planned duration of approximately 24-36 months with interim analysis planned at 100 patients before further enrollment will be considered. Statistical hypotheses are not intended for this registry and descriptive analysis will be conducted. Data from all clinical sites are intended to be pooled for analysis. It is possible that sub-analyses may be conducted to demonstrate VeriSight guidance for target intervention types in structural heart and electrophysiology procedures.

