5.3.2 Secondary Efficacy Variables

Secondary analyses will include the following:

- a) Procedural characterization when using VeriSight measured by
 - i. type of procedure utilizing ICE imaging
 - ii. total procedural room time (door-in to door-out, mins), total procedure time (skin to skin, mins)
 - iii. total fluoroscopy time (mins)
 - iv. total contrast volume used (cc), fluoroscopic dosage (mGy)
 - v. ability to image from the right side of the heart for a left sided intervention
 - vi. TEE usage rate and avoidance of TEE procedure
 - vii. Other imaging modality used during the procedure
 - viii. Change in management from use of VeriSight – need for high risk patient and/or procedure management
 - ix. Duration and type of anesthesia
 - x. Freedom from general anesthesia
- b) Device characterization when using VeriSight based on a scoring scale for the physical attributes of the VeriSight catheter
- c) Physician survey regarding the Philips ICE using a five-point ordinal Likert-type rating scale
- d) Staff survey regarding the Philips ICE using a five-point ordinal Likert-type rating scale

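### The usability rating against usual imaging has no neutral level and two favourable levels out of three, so a rater who sees no difference cannot say so

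*Protocol*

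**What the plan says.** Protocol 6.6 describes two ratings of the same items, followed by a survey.

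- **Rating of VeriSight itself.** Handling, EPIQ navigation and imaging modality are scored on four levels from poor to excellent.
- **Comparative rating.** The investigator "will evaluate the same physical characteristics of the catheter, ultrasound system navigation, and imaging modality", this time "based on their own clinical experiences of imaging that would have been generally used during the procedure". The levels are given in one sentence: "This rating score is defined as inferior, better, superior". The ratings "will be gathered at first enrollment, 10th enrollment, and last enrollment at each participating site".
- **Physician and staff survey.** Claim statements are answered on a five-point ordinal scale. Answers draw on registry experience and on experience with other ICE products or modalities such as TEE.

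SAP 5.3.2 lists as a secondary variable "Device characterization when using VeriSight based on a scoring scale for the physical attributes of the VeriSight catheter". It does not give the levels of the comparative rating, add a neutral one, or say how a tie is recorded. SAP 8.2 summarises categorical data by frequencies and percentages. For ordinal Likert data it uses the median, proportions, mode and a bar chart. SAP 8.2.2 says the impact of missing data will not be assessed.

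Protocol 3.1 says no specific claims are being validated, but that "data analyzed from this protocol are intended to inform of future claims regarding the performance and safety of the VeriSight catheter".

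**The concern.** A comparative scale should let a rater say that two things are alike. This one does not, and the two ways of favouring VeriSight outnumber the one way of disfavouring it. *Better* and *superior* are also not clearly separate steps.

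The registry has no control arm and no hypothesis test, so for an item like this the printed percentages are the result. A favourable percentage from a scale that cannot record no difference is easy for a reader to discount, and the lost neutral answers cannot be recovered afterwards. The bias controls in Protocol 3.3 and SAP 4.5 (multiple sites, training, standard forms, monitoring) do not touch this, because every site would use the same scale.

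**Working it through.** The documents give no sample size, rate or precision for this rating, so there is no plan figure to reproduce.

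**Step 1: count the levels.** The comparative scale in Protocol 6.6 has 1 unfavourable, 0 neutral and 2 favourable levels.

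**Step 2: look for a neutral level elsewhere.**
- The poor-to-excellent scale rates VeriSight on its own.
- The five-point scale belongs to the separate survey.
- The SAP does not list the comparative levels.

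None of these supplies a neutral level for the comparison.

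**Step 3: what happens to raters who see no difference (illustration).** All inputs here are assumptions; the documents give neither q nor s.
- q = share of raters who see no difference. The rest split evenly between worse and better, so true net preference is zero.
- s = share of those neutral raters who mark *better* or *superior*.
- Every rater answers.

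Formulas:
- recorded favourable share F = (1 − q)/2 + q·s
- recorded inferior share I = (1 − q)/2 + q·(1 − s)
- inflation of the favourable share = F − (1 − q)/2 = q·s
- spurious net preference = F − I = q·(2s − 1)

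With q = 0.50 (true opinion 25/50/25):
- s = 1/2, even split: F = 0.25 + 0.25 = 50%; net = 0.50 × 0 = 0.
- s = 2/3, random marking of three labels: F = 0.25 + 0.333 = 58%; net = 0.50 × 0.333 = +17 points.
- s = 1, all favourable: F = 0.25 + 0.50 = 75%; net = 0.50 × 1 = +50 points.

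Other values, as favourable share / net points:

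| q | true favourable | s = 1/3 | s = 1/2 | s = 2/3 | s = 1 |
|---|---|---|---|---|---|
| 0.2 | 40% | 47% / −7 | 50% / 0 | 53% / +7 | 60% / +20 |
| 0.4 | 30% | 43% / −13 | 50% / 0 | 57% / +13 | 70% / +40 |
| 0.6 | 20% | 40% / −20 | 50% / 0 | 60% / +20 | 80% / +60 |

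In every cell the recorded favourable share exceeds the true one. The net preference moves towards VeriSight only when s is above 1/2.

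**Step 4: blanks.** If all neutral raters skip the item, the 25/50/25 case gives 25/(25 + 25) = 50% favourable among those who answered. Half the ratings are then missing, and the SAP does not plan to examine that.

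**Step 5: after the fix.** With an equivalent level, neutral raters add to neither side. The 25/50/25 case is recorded as 25/50/25, with net preference 0 for any q.

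**The case against.** The case against giving this much weight is good in several respects.

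- **Net direction is not proven.** A reader might infer that the result is biased towards VeriSight. The documents do not establish that: an even split of neutral raters leaves the net preference unbiased, and at q = 0.4 the range runs from −13 to +40 points depending on s. What stands is that any neutral rater who marks a favourable level inflates the favourable share. A lean towards VeriSight is probable from the two-to-one layout, but not demonstrated.
- **It is not shown to be the only comparison with usual imaging.** A reader might take it as such. The survey also draws on experience with other modalities, and its statements are not reproduced in the protocol.
- **No pooled favourable share is planned.** Neither document merges *better* with *superior*, and SAP 8.2 already reports frequencies or proportions. The inflated figure appears only if someone adds the two levels, although each level's own percentage also absorbs misplaced neutral answers.
- **The link to a named endpoint is uncertain.** The SAP speaks of a scoring scale, which is Protocol 6.6's term for the poor-to-excellent instrument; the comparison is called a rating score. The SAP may not cover the comparison at all. That is a reason to name it there.
- **The stakes are limited.** The same sentence of Protocol 3.1 says no claims are being validated, and what it expects to inform is performance and safety claims.

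None of this supplies the missing neutral level.

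**Conclusion.** The point holds as a modest, cheaply corrected flaw in a descriptive usability rating. As written, the scale misrecords or loses every rater who sees no difference. In the 25/50/25 illustration the recorded favourable share is 50% to 75% for s between 1/2 and 1, against a true 25%, and net preference is shifted by 0 to +50 points. These figures rest on assumed q and s and show a possible range, not an estimate. More ratings would not help, since the number of ratings does not enter the formulas.

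One reading is also assumed: that VeriSight is the item rated and usual imaging is the reference. That is the natural sense of Section 6.6, though it is not stated outright.

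The documents do not support extending the point to the main results. The technical, imaging, clinical and safety analyses do not use this rating.

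**What to change.** 1. **Protocol 6.6 and the rating form:** replace the three levels with a balanced scale that has a neutral level, for example inferior / equivalent / superior, or a symmetric five-level version. Say explicitly that VeriSight is rated against usual imaging.
2. **SAP 5.3.2 and 8.2:** name this rating separately from the poor-to-excellent scale, report every level, and count only levels above *equivalent* as favourable. Report the number of blanks.
3. **Ratings already taken on the present scale, if any:** report them separately and by level, do not merge *better* and *superior* into a preference rate, and state that no neutral option was offered.

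The cost is one protocol line, one form update and a short SAP addition. Ratings from the two scales cannot be pooled, and the first / 10th / last sequence is broken at sites that have already started. The favourable share may also come out lower. If a change is no longer practical, step 3 alone removes much of the risk of misreading but does not recover the neutral answers.

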7. SAFETY EVENTS: DEFINITIONS AND REPORTING

7.1. Definition

Adverse Event (AE) - any untoward medical occurrence, unintended disease or injury, or untoward clinical signs (including abnormal laboratory findings) in subjects during registry participation, which does not necessarily have a causal relationship with the VeriSight device or procedures.

Serious Adverse Events (SAE) - defined as an AE that:

- Led to Death
- Are Life-threatening
- Led to Hospitalization (in-patient or prolonged)
- Resulted in Disability or Permanent Damage
- Led to Fetal Distress, Fetal Death or Congenital Anomaly/Birth Defect
- Required Intervention to Prevent Permanent Impairment or Damage

NOTE: Planned hospitalization for a pre-existing condition, or a procedure required by the clinical investigational plan, without serious deterioration in health, is not considered an SAE.

Adverse Device Event (ADE) - an AE related to the use of a medical device. This definition includes AEs resulting from insufficient or inadequate instructions for use, deployment, implantation, installation, or operation, or any malfunction of the VeriSight catheter. This definition also includes any event resulting from use error or from intentional misuse of the medical device.

Serious Adverse Device Effect (SADE) - adverse device effect that has resulted in any of the consequences characteristic of a serious adverse event

Unanticipated Serious Adverse Device Effect (USADE) - serious adverse device effect which by its nature, incidence, severity or outcome has not been identified in the current version of the risk analysis report

Note: anticipated serious adverse device effects (ASADE) is an effect which by its nature, incidence, severity or outcome has been identified in the risk analysis report

Document ID:	IGT_IGD_ICE Registry Study 2019 10745	Document title:		Classification:	Confidential
Modified:	24 APR 2021	Philips ICE Registry			
Version:	2.0	User Tool ID:	16.2.6UserTool0004	Page:	24
Status:	Final	User Tool Version Date	30May2019		

Clinical Registry Protocol
IGT_IGD_ICE Registry Study_2019_10745

Device Deficiency - inadequacy of a medical device with respect to its identity, quality, durability, reliability, safety or performance such as malfunctions, misuse or use errors and inadequate labeling

